4.2.2 Tumor response

In consideration of the decision to terminate enrolment prior to the completion and the limited number of evaluable patients, the efficacy analysis will be reduced and tumor assessment details will only be listed for all subjects assigned to study intervention. Listings will include the following endpoints:

- Progression free survival (PFS)
- Overall survival (OS)
- Best objective response (BOR)
- Change in TL tumor size

4.2.3 Safety

Unless stated otherwise, all analyses described in following subsections will be based on Safety analysis population.

4.2.3.1 Exposure

Exposure to study intervention (i.e. the total amount of study drug received) and dose modification data will be listed for all subjects.

Total treatment duration (weeks) will be summarized by study interventions by the following: mean, standard deviation, minimum, maximum, median, number of observations and total treatment years.

Number of treatment cycles received will be summarized by study intervention by mean, median and lower and upper quartile. The number and percentages of subjects receiving none and more than x cycles (x=1, 2, 3 ...) will be presented.

Actual treatment duration (weeks) and dose intensity of investigational products will be summarized using mean, standard deviation, median, and quartiles as well as the minimum and maximum values.

Dosing deviations for study interventions will be summarized with reasons for deviations for the following categories: treatment interruptions, dose reductions (not applicable for durvalumab administration) and cycle delays.

4.2.3.2 Adverse events

Data from all cycles (of induction and maintenance phase) will be presented separately as well as combined.

The majority of the AE summaries, unless stated otherwise, will be based on TEAEs. See section 3.2.3.3 for definition of treatment emergence. Any AE occurring within the defined 90-day follow-up period after discontinuation of study intervention will be included in the AE summaries. Any AEs in this period that occur after a subject has received further therapy for cancer (following discontinuation of study intervention) will be flagged in the data listings and will be excluded from above summaries. Numbers and percentages of subjects will be presented for all AEs, AEs with grade ≥ 3 , AEs grade 5, possibly related AEs, possibly related AEs with grade ≥ 3 , possibly related AEs with grade 5, serious AEs and possibly related serious AEs.

AEs occurring prior to first dose of investigational product (i.e. before study Day 1), or after the 90-day follow-up period after discontinuation of investigational product will be listed.

An overall summary table of the number of subjects experiencing each category of AE will be produced. Following categories will be included:

- Any AE
- Any AE of CTCAE grade 3 or higher
- Any AE with outcome = death
- Any SAE (including events with outcome = death)
- Any SAE leading to discontinuation of treatment
- Any AE leading to discontinuation of treatment
- Any AE leading to reduction of treatment
- Any AE leading to dose interruption of treatment
- Any AE leading to modification of treatment (either an interruption and/or a dose reduction)
- Any AESI or AEPI

Except for any AE leading to reduction, dose interruption or modification of treatment and any other significant AE, all categories will be duplicated as applicable to add the condition of being possibly related to treatment (overall and separately for etoposide or cisplatin/carboplatin, etoposide or cisplatin/carboplatin or durvalumab, durvalumab, AZD2811, durvalumab or AZD2811).

Besides the overall summary table, following presentations of number of subjects experiencing TEAEs and of number of AEs will be presented:

- Number of subjects with AEs by SOC and PT
- Number of AEs by SOC and PT
- Number of subjects with AEs, most common (frequency of $>10\%$) by PT
- Number of subjects with AEs by SOC, PT and maximum reported CTCAE grade
- Number of subjects with AEs of CTCAE grade 3 or higher by SOC and PT
- Number of subjects with AEs, assessed by investigator as possibly related to study intervention by SOC, PT and maximum reported CTCAE grade
- Number of subjects with AEs of CTCAE grade 3 or higher, assessed by investigator as possibly related to study intervention by system organ class and preferred term
- Number of subjects with AEs leading to dose reduction by IP by SOC and PT
- Number of subjects with AEs leading to dose interruptions by IP by SOC and PT
- Number of subjects with AEs leading to dose modifications by IP by SOC and PT
- Number of subjects with AEs with outcome of death by SOC and PT
- Number of subjects with SAEs by SOC and PT
- Number of SAEs by SOC and PT

- Number of subjects with SAEs, assessed by investigator as possibly related to study intervention by SOC and PT
- Number of subjects with AEs leading to discontinuation of IP by SOC and PT
- Number of SAEs by SOC and PT

Details of any deaths will be listed for all subjects (Enrolled). For Safety set, the number and percentages of subjects of deaths will be presented by death categories (death related to disease under investigation only, AE with outcome of death only, AE with outcome of death only (AE start date falling after 90 day follow up), number of subjects with death related to disease and an AE with outcome of death, other deaths).

A list of PTs provided by AZ will be used to identify AESIs and AEPIs. Presentations will be provided for AESIs/AEPIs by SOC and PT.

Key subject information will be provided for SAEs, AESIs/ and AEPIs including flag for imAEs, which will be identified as described in Section 3.2.3.4.

In order to distinguish between AESIs and AEPIs, PTs for AEPIs will be flagged in all AESI/AEPI outputs.

A summary for non-serious AEs occurring in greater than 5% of subjects will be prepared for Food and Drug Administration, but will not be part of the CSR.

All AE data will be listed for several populations:

- Safety
- Safety, subjects with subsequent therapy within 90 days after end of study treatment
- Enrolled, subject who were not exposed to treatment

AESIs will be listed (Safety) including flag for AEPI and imAE.

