9.4.2 Efficacy

From CSP v8.0 onwards, the starting dose of AZD2811 in the maintenance phase was CCI [REDACTED], the study will therefore primarily report efficacy for the CCI [REDACTED] AZD2811 dose. Further sensitivity analyses will be defined in the SAP.

From CSP v9.0 onwards, study enrolment has been terminated and the study will proceed to final analysis and an abbreviated CSR. As a result of this, efficacy analyses will be streamlined as there were too few patients who received AZD2811 in combination with durvalumab (9 patients) to give meaningful analyses.

Sections below containing original plans for reporting efficacy are retained for reference but notable changes will include:

- No summaries of efficacy data will be provided, with the exception of PK, and selected efficacy data will be listed only.
- DoR, PFS2, PRO and breakthrough pain therapy endpoints will no longer be reported in the abbreviated CSR.

Full details of planned efficacy analyses will be documented in the SAP.

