9.4.4 Safety

From CSP v9.0 onwards, study enrolment has been terminated and the study will proceed to an abbreviated CSR. The abbreviated CSR will present a full safety report and as such the analysis of safety endpoints will remain largely unchanged. Any changes to the planned analyses below will be fully described in the SAP and will be limited to instances where, in light of the early termination of enrolment, listings of specific data points are more appropriate than summaries.

Safety and tolerability will be assessed in terms of AEs (including SAEs), deaths, laboratory data, vital signs, ECGs, physical examination, and exposure. These will be collected for all participants. Data from all cycles of study intervention will be combined in the presentation of safety data, along with summaries of the induction phase and the maintenance phase unless

otherwise specified. Safety analyses will be performed using the safety analysis set. Safety data will be presented using descriptive statistics. Analyses will be presented for the overall study and separately for the induction and maintenance phases.

From CSP v8.0 onwards, the patients who were transitioned onto the maintenance phase received ~~CCI~~ of AZD2811, and the study will therefore report efficacy and safety by maintenance phase starting dose of AZD2811 as applicable. Further details will be provided in the SAP. In general, the baseline value for statistical analysis is the last non-missing value prior to administration of the first dose of study intervention in the induction phase. Details will be described in the SAP.

Adverse Events

Adverse events will be coded using the most recent version of the Medical Dictionary for Regulatory Activities (MedDRA) that will have been released for application by AstraZeneca/designee.

“On treatment” will be defined as assessments between date of start dose of study intervention in the induction phase and 90 days following discontinuation of study intervention (90 days after the last dose of AZD2811 + durvalumab or durvalumab + EP). For AEs, on treatment (or treatment-emergent AEs [TEAEs]), will be defined as any AEs that started after dosing or prior to dosing and which worsen following exposure to study intervention.

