Adverse events observed up until 90 days following discontinuation of study intervention (ie, 90 days after the last dose of AZD2811 + durvalumab or durvalumab + EP) or until the initiation of the first subsequent therapy following discontinuation of study intervention (whichever occurs first) will be used for reporting of AE summary tables. This will more accurately depict AEs attributable to study treatment only because a number of AEs up to 90 days following discontinuation of study intervention are likely to be attributable to subsequent therapy. However, to assess the longer term toxicity profile, AE summaries will also be produced containing AEs observed up until 90 days following discontinuation of study intervention (ie, without taking subsequent therapy into account).

Any events in this phase that occur after a participant has received further therapy for cancer (following discontinuation of study intervention) will be flagged in the data listings.

A separate data listing of AEs occurring more than 90 days after discontinuation of study intervention will be produced if required. These events will not be included in AE summaries.

Adverse events will be presented by MedDRA system organ class, MedDRA preferred term, and CTCAE grade, including the number and percentage of participants reporting at least one event, number of events, and exposure adjusted rates, where appropriate.

An overview of AEs will be presented for each phase, including the number and percentage of participants with any AE, AEs with outcome of death, SAEs, and AEs leading to discontinuation of study intervention.

Separate AE tables will be provided, taking into consideration the relationship with study intervention assessed by the investigator, CTCAE grade, seriousness, death, and events leading to discontinuation of study intervention, as well as other action taken related to study intervention.

Dose-limiting toxicities will be displayed in the listing for the DLT-evaluable participant population.

Full details of AE analyses will be provided in the SAP.

Treatment Emergent

The following events are considered treatment emergent:

- Adverse events with an onset date on or after the first dose of study intervention
- Worsening of pre-existing events on or after the first dose of study intervention

Clinical Laboratory Safety Assessments

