9.4.7 Pharmacokinetic Analyses

For each analyte, whole blood or serum concentrations for each scheduled time point will be summarized by visit using appropriate descriptive statistics. Protocol scheduled times will be used to present the PK concentration summary tables and corresponding geometric mean concentration-time figures. Additional details for the handling of non-quantifiable concentrations will be included in the SAP.

- The geometric mean (gmean, calculated as $\exp[\mu]$, where μ is the mean of the data on a logarithmic scale)

- $\text{gmean} \pm \text{geometric standard deviation}$ ($\text{gmean} + \text{gstandard deviation}$ and $\text{gmean} - \text{gstandard deviation}$), which are calculated as $\exp(\mu \pm s)$
- CV, calculated as $100 \sqrt{\exp[s^2] - 1}$, where s is the standard deviation of the data on a log scale
- $\text{gmean} \pm \text{standard deviation}$ (calculated as $\exp[\mu \pm s]$)
- Arithmetic mean, calculated using untransformed data
- Standard deviation, calculated using untransformed data
- Minimum
- Maximum
- Number of observations
- Number of participants below lower limit of quantification

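### SAP edition 2 departs from protocol v9.0 on three outputs (full 90-day AE summaries, a durvalumab concentration summary, a DLT listing), and the readable text of Section 6 does not record it

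*SAP*

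**What the plan says.** **Protocol v9.0.** Section 9.4.4 promises a full safety report with largely unchanged analyses. It adds: "Any changes to the planned analyses below will be fully described in the SAP", and limits such changes to cases where early termination makes a listing more suitable than a summary. The main AE tables stop at 90 days after discontinuation or at first subsequent therapy, whichever is earlier. To show longer-term toxicity, "AE summaries will also be produced containing AEs observed up until 90 days following discontinuation of study intervention", that is, "without taking subsequent therapy into account". The same section says: "Dose-limiting toxicities will be displayed in the listing for the DLT-evaluable participant population".

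On pharmacokinetics, Section 9.4.2 says: "No summaries of efficacy data will be provided, with the exception of PK, and selected efficacy data will be listed only". Section 9.4.7 says: "For each analyte, whole blood or serum concentrations for each scheduled time point will be summarized by visit". Durvalumab is the serum analyte.

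**SAP edition 2.** Section 4.2.3.2 includes AEs from the 90-day follow-up in the summaries, but those arising after further cancer therapy "will be flagged in the data listings and will be excluded from above summaries". Section 4.2.4.1 summarizes AZD2811 concentrations and lists durvalumab. Section 4.2 describes Appendix A as the complete list of planned outputs. Section 6, on changes from the protocol, has three items: laboratory shift tables, dose interruptions and reductions by cycle length, and a partly redacted clarification about reduced efficacy reporting.

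**The concern.** Safety is the stated focus of the abbreviated CSR, and PK is the one area exempted from listing-only reporting. A programmer who follows the SAP exactly would produce AE tables that stop at subsequent therapy, so the longer-term picture the protocol wanted summarized could be had only by reading a listing. The durvalumab half of a secondary PK objective would have no summary. How DLT status was recorded would not be shown as a separate output.

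Section 6 does record departures of similar or smaller size, such as how laboratory shifts are tabulated. A reader would expect these three to appear there too, with a reason.

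**Working it through.** There is no planned figure to reproduce. The check compares what the protocol asks for with what the SAP plans.

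| Output | Protocol v9.0 | SAP edition 2 | Named in readable Section 6? |
|---|---|---|---|
| AE summaries over the full 90 days | 9.4.4: a second set, besides the one cut at subsequent therapy | 4.2.3.2: one set, with AEs after further therapy excluded; listing 16.2.7.2 covers those subjects | No |
| Durvalumab concentrations | 9.4.7: by-visit summary for each analyte; 9.4.2 keeps PK summaries | 4.2.4.1: listed only (16.2.6.2.2) | No |
| DLTs | 9.4.4: listing for DLT-evaluable participants | Abbreviation list only; no such set in Table 2, no output in Appendix A | No |

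**Count from Appendix A.** AE count tables for the abbreviated CSR:
- 14.3.2.1, .2, .3, .5, .6, .7, .9, .10, .11, .12 and .13: 11
- 14.3.3.1.2: 1
- 14.3.4.1.1 to .3: 3
- 14.3.5.1: 1
- 14.3.6.2: 1

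Total: 11 + 1 + 3 + 1 + 1 = 17. None is specified as a full 90-day version. The count leaves out key-information listings, the preferred-term list, the FDA-only table and the All Deaths table. The last has a category for AEs starting after the 90-day window, so it does not follow the AE-table cut.

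PK outputs are Table 14.2.2.1 and Figures 14.2.2.1 to 14.2.2.4, all for AZD2811 or its metabolite. Durvalumab has no table and no figure. There is no DLT output.

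**Does the protocol's own allowance cover these?**
- *AE summaries:* it could, since a summary may become a listing. But the SAP does not present the single set as a change from the protocol or link it to early termination.
- *Durvalumab:* no. The allowance belongs to the safety section, and 9.4.2 exempts PK from listing-only reporting. The SAP's own PK set also admits participants with durvalumab concentrations only.
- *DLTs:* no. The allowance replaces summaries with listings; it does not remove a listing.

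**If the exclusion in 4.2.3.2 is read narrowly**, so that some tables keep the later events, the cut-off versions of those tables are missing instead. Either way, only one of the two sets is planned.

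**The case against.** The strongest reply is that the protocol leaves room for this. Section 9 says v8.0 text is kept for reference, with full details to come in the SAP, and 9.4.4 allows listings in place of summaries. Neither passage requires a change to be entered in Section 6. The AE exclusion and the durvalumab listing are both stated openly in the SAP. This largely stands: the protocol's requirements are not absolute, and the first two items are not hidden. What is missing is the statement that they are changes, and the reason.

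It also stands that the protocol itself regards the tables cut at subsequent therapy as the better picture of AEs attributable to study treatment, and the SAP keeps those. Durvalumab sampling in the readable maintenance schedule is sparse and predose, so a listing conveys much of it. The DLT listing is probably empty: protocol 4.1.2.2.1 reports no DLT in the first six participants, and the further run-in cohort depended on v8.0, which was never implemented. It would still have some documentary value, because the same section reports two fatal SAEs that investigators attributed to AZD2811.

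Two stronger readings are tempting. A reader might infer that safety information is lost. It is not: AEs are listed in 16.2.7.1 and 16.2.7.2, and durvalumab concentrations in 16.2.6.2.2. A reader might also count exposure-adjusted AE rates as a fourth omission. The protocol makes those conditional ("number of events, and exposure adjusted rates, where appropriate"), and SAP 4.2.3.1 summarizes total treatment years, so the documents do not support that.

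**Conclusion.** The point holds as a mismatch between the two documents that should be corrected. Three outputs are called for in protocol v9.0; none is planned in the form described, and none is named in the readable text of Section 6. Two are reduced to listings and one is absent.

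The AE item matters most, because the report is meant to present safety in full. Its size cannot be stated: the documents do not say how many patients start new therapy within 90 days of last dose, or when. For everyone else the two sets of summaries coincide. The durvalumab item is a clear conflict of limited consequence. The DLT item is the smallest.

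No numerical bias is shown, and it would go too far to infer that the safety conclusions are unreliable. The conclusion assumes that Appendix A is complete, as SAP 4.2 says, and that no redacted text records these decisions. Relevant redactions are in SAP Section 1 (what is handled outside the CSR), the 4.2.4 heading and text above the PK section, and Section 6 item 3.

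**What to change.** 1. In SAP 4.2.3.2 and Appendix A, repeat Tables 14.3.2.1 and 14.3.2.2 over the full 90 days without the subsequent-therapy exclusion, using the flag already defined in 3.2.3.4.
2. In SAP 4.2.4.1 and Appendix A, add a by-visit serum durvalumab summary on the existing PK set, with the statistics already chosen for AZD2811 and the quantification-limit rules in 3.2.3.3.
3. Add the DLT listing, using the definitions in protocol 4.1.3 and 4.1.4, and state that there were none if it is empty.
4. If any of these is dropped on purpose, say so in Section 6 with the reason.

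The cost is three tables and one short listing from data already collected, or a few lines of text for whatever is dropped. The abbreviated CSR becomes slightly longer. The SAP edition is dated 05 May 2022 and the data cut-off was planned for 18 June 2022, so the change could have been made before the cut-off.

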4.2.3.3 Laboratory

Clinical chemistry, coagulation and hematology results and change from baseline will be summarized using descriptive statistics (number of observations, mean, standard deviation, minimum, lower quartile, median, upper quartile and maximum) at each scheduled assessment time for continuous laboratory assessments). For a subset of laboratory variables (see Section 3.2.3.5) included in the current version of CTCAE, the CTCAE grade change from baseline to maximum on treatment will be summarized by phase. Urinalysis results will be listed only.

Number and percentages of clinically important changes will be presented by clinical chemistry, coagulation and hematology parameter.

Proportions of subjects with elevated liver test (elevated alanine aminotransferase (ALT) or aspartate aminotransferase (AST) (≥ 3 ULN), and elevated Total bilirubin ($\geq 2x$ ULN)) will be summarized and individual subject data for subjects with potential Hy's law will be provided.

Key subject information will be also provided for subjects with treatment-emergent clinical chemistry, coagulation or hematology values outside predefined criteria.

Plots for ALT and AST versus total bilirubin, expressed as multiples of upper limit of normal (ULN) and liver biochemistry test results over time will be created. The reference lines are 3x ULN for ALT, AST, and 2x ULN for Total bilirubin. In each plot, total bilirubin will be in the vertical axis.

Laboratory reference ranges as well as all individual laboratory data will be listed. Liver assessments, liver risk factors and liver signs and symptoms for all potential Hy's law cases will be listed separately.

4.2.3.4 Vital signs

Vital sign results and change from baseline will be summarized over time, height is collected only at screening. Vital sign results outside reference limits will be presented along with key subject information for subjects who experience these results.

Vital signs values will be classified as normal (if value is within normal reference range), low (if value is below the normal reference range), and high (if value is above the normal reference range) according to the normal reference ranges below.

Table 7 Vital Signs Reference Ranges

Parameter	Low /Normal / High
Temperature	<36.0 C / 36.0-37.5 C / >37.5 C
Pulse	<60 / 60-100 / >100
Systolic blood pressure	<90mmHg / 90 -140mmHg / >140mmHg
Diastolic blood pressure	<60mmHg / 60 -90mmHg / >90mmHg
Respiratory rate	<12/min/ 12-20/min/ >20/min
Saturation of peripheral oxygen (SpO2)	<94%/ 94-100%/ NA

All individual vital signs data will be listed. Baseline weight, height and BMI data will be listed along with baseline characteristics. Additionally, weight and BMI will be listed by time point separately.

Physical examination results will be listed only.

